2.16.6 Optical Coherence Tomography Angiography (OCTA)

OCTA is optional at sites that have an OCTA. The OCTA needs to be performed by a qualified technician following an acquisition protocol of the central reading center at Visits 1 and 8, as scheduled in the SoA (Section 2.15.1). The specifications of this OCTA can be found in the acquisition protocol of the central reading center. Images obtained via OCTA will be sent to the Central Reading Center for evaluation. Several quantitative and qualitative parameters, including the FAZ and area of nonperfusion, which have been shown to be associated with DR severity, will be assessed.

2.16.7 *Slit Lamp Biomicroscopy (Anterior and Posterior Segment)*

The slit lamp examination (anterior and posterior segment) will be performed according to local medical practice and applicable medical standards at the site at every visit, as stated in the SoA ([Section 2.15.1](#)). Abnormal findings are to be recorded in the eCRF as either medical history or AE, as applicable.

2.16.8 *Tonometry (Intraocular Pressure (IOP) Measurement)*

IOP is to be measured at every visit with any locally approved non-contact tonometer.

If there is no non-contact tonometer available at the site, applanation tonometry (Goldmann, Tonopen, or other locally approved alternatives) may be used. In any case, where both methods are available, the non-contact method is to be used. In cases in which Goldmann applanation tonometry (GAT) is used, assessment of corneal health using fluorescein stain should be performed prior to tonometer applanation.

The same method of IOP measurement must be used throughout the study for each individual participant and should be performed at approximately the same time of day, if possible. Values, including time of day and measuring type, are to be recorded in the eCRF.

2.16.9 *Vision-threatening Complications*

VTC is defined as the composite outcome of PDR (inclusive of participants who have vitreous hemorrhage or tractional retinal detachment believed to be due to PDR) and/or ASNV identified by Investigators (participants with neovascularization of the iris [at least 2 cumulative clock hours], and/or definitive neovascularization of the iridocorneal angle) and/or CI-DME as defined in [Section 2.16.10](#) below.

VTCs are defined as occurrence of any of the following AEs:

- More than mild PDR (DRSS 65 and above)
- Iris neo-vascularization
- CI-DME

2.16.10 *DME and CI-DME*

DME is defined as fluid in the macula.

CI-DME is defined as the presence of fluid in the central subfield in participants who have no fluid at baseline or CST > 325 μm .

The assessment will be continued after treatment discontinuation until end of study.

2.17 Safety Assessments

Safety will be assessed, and TEAEs recorded (as indicated) at every visit.

2.17.1 Physical Examination

A physical examination (by means of inspection, palpation, auscultation) will be performed at Screening (Visit 1) as described in the SoA ([Section 2.15.1](#)) by a physician at the study site and will cover at least the organs of the cardiovascular, respiratory, and abdominal systems; measuring body temperature will be included. Abnormal physical examination findings are recorded either as medical history or as AEs in the eCRF. Body weight will be measured by a member of the investigator's team. The body mass index (BMI) will be calculated by Data Management or the eCRF based on weight and height.

2.17.2 Vital Signs

Pulse rate and systolic / diastolic blood pressure will be measured repeatedly as outlined in the SoA ([Section 2.15.1](#)). Blood pressure and heart rate will be measured in a supine or semi supine position after ≥ 5 minutes rest. Blood pressure and heart rate should always be measured before blood draws when scheduled at the same time point.

2.17.3 Clinical Safety Laboratory Assessments

A lab assessment (hematology, blood chemistry, urinalysis, and HbA1c) will be performed at Screening (Visit 1) and at Week 24 (Visit 8) as described in the SoA ([Section 2.15.1](#)). Blood and urine samples will be taken. See [Section 3.3](#) for a table of clinical laboratory tests to be performed.

The investigator must review the laboratory report, document this review, and record any clinically significant changes, including any lab test that was in the age-adjusted normal range and became abnormal at EOS, occurring during the study as an AE. The laboratory reports must be filed with the source documents.

Abnormal laboratory findings associated with the underlying disease are not considered clinically significant unless judged by the investigator to be more severe than expected for the participant's condition.

All laboratory tests with values considered clinically significantly abnormal during participation in the study or within one month after the last dose of study intervention should be repeated until the values return to normal or BL or are no longer considered clinically significant by the investigator or the medical monitor.

If such values do not return to normal/BL within a period of time judged reasonable by the investigator, the etiology should be identified, and the sponsor notified.

All protocol-required laboratory tests must be conducted in accordance with the laboratory manual and the SoA ([Section 2.15.1](#)). If laboratory values from non-protocol specified laboratory tests performed at the institution's local laboratory require a change in participant

management or are considered clinically significant by the investigator (eg, SAE or AE or dose modification), then the results must be recorded.

2.17.4 *Pregnancy Testing*

Both urine and serum β -hCG pregnancy tests are planned to be conducted in woman of childbearing potential enrolled in this clinical study. A serum test is planned at Screening (Visit 1); during all other visits, urine tests will be performed. Dip stick urine pregnancy tests allow the investigator to take action while the participant is at site in case of a positive test.

If the urine pregnancy test is positive, the study medication should be discontinued immediately. The urine pregnancy test results should be however confirmed using a serum pregnancy test at a local lab before permanently discontinuing the participant from the study.

2.18 *Adverse Events (AEs), Serious Adverse Events (SAEs), and Other Safety Reporting*

The definitions of AEs and SAEs can be found in [Appendix 3](#) and will conform to the current Medical Dictionary for Regulatory Activities (MedDRA) standard.

AEs will be reported by the participant (or, when appropriate, by a caregiver, surrogate, or the participant's legally authorized representative).

The Investigator and any qualified designees are responsible for detecting, documenting, and recording events that meet the definition of an AE or SAE and remain responsible for following up on all AEs reported during the study until resolution or until the end of the study.

2.18.1 *Time Period and Frequency for Collecting AE and SAE Information*

All AEs/SAEs will be collected from the signing of the ICF until end of study.

All SAEs will be recorded and reported to the sponsor or designee immediately and under no circumstance should this exceed 24 hours of learning of the event, as indicated in [Section 2.21.5](#). The investigator will submit any updated SAE data to the sponsor within 24 hours of it being available.

TEAEs will be defined as those AEs that occurred after first dosing and those existing pre-dose AEs that worsened in severity post-dose during the main treatment period until the end of study.

Investigators are not obligated to actively seek information on AEs or SAEs after conclusion of the study participation/the End-of-Study visit. However, if the investigator learns of any AE/SAE, including a death, at any time after a participant has been discharged from the study, and he/she considers the event to be reasonably related to the study intervention or study participation, the investigator must promptly notify the sponsor.

2.18.2 *Method of Detecting AEs and SAEs*

Care will be taken not to introduce bias when detecting AEs and/or SAEs. Open-ended and non-leading verbal questioning of the participant is the preferred method to inquire about AE occurrences.

2.18.3 *Follow-up of AEs and SAEs*

After the initial AE/SAE report, the investigator is required to proactively follow each participant at subsequent visits/contacts. All SAEs, and AEs of special interest (as defined in [Section 2.18.6](#)), will be followed until resolution, stabilization, the event is otherwise explained, or the participant is lost to follow-up (as defined in [Section 2.14.12](#)). Further information on follow-up procedures is provided in [Appendix 4](#).

2.18.4 *Regulatory Reporting Requirements for SAEs*

- Prompt notification by the investigator to the sponsor of an SAE is essential so that legal obligations and ethical responsibilities towards the safety of participants and the safety of a study intervention under clinical investigation are met.
- The sponsor has a legal responsibility to notify both the local regulatory authority and other regulatory agencies about the safety of a study intervention under clinical investigation. The Sponsor will comply with country-specific regulatory requirements relating to safety reporting to the regulatory authority, Institutional Review Board (IRB)/ Independent Ethics Committee (IEC), and Investigators.
- An investigator who receives an investigator safety report describing an SAE or other specific safety information (eg, summary or listing of SAEs) from the sponsor will review and then file it and will notify the IRB/IEC, if appropriate according to local requirements.
- For all studies, investigator safety reports must be prepared for suspected unexpected serious adverse reactions (SUSARs) according to local regulatory requirements and sponsor policy and forwarded to investigators as necessary.

2.18.5 *Pregnancy*

- Details of all pregnancies in female participants and, female partners of male participants will be collected after the start of study intervention and until the end-of study visit.
- If a pregnancy is reported, the investigator will record pregnancy information on the appropriate form and submit it to the Sponsor within 24 hours after obtaining the necessary signed informed consents from the pregnant participant. Study medication should be discontinued immediately upon receipt of a positive pregnancy test.

- While pregnancy itself is not considered to be an AE or SAE, any pregnancy complication or elective termination of a pregnancy for medical reasons will be reported as an AE or SAE.
- Abnormal pregnancy outcomes (eg, spontaneous abortion, fetal death, stillbirth, congenital anomalies, ectopic pregnancy) are considered SAEs, and will be reported as such.
- The participant /pregnant female partner will be followed to determine the outcome of the pregnancy. The investigator will collect follow-up information on the participant/pregnant female partner and the neonate, and the information will be forwarded to the sponsor.
- Any female participant who becomes pregnant while participating in the study will discontinue study intervention.

2.18.6 *Adverse Events of Special Interest (AESI)*

AESI must be reported to the Sponsor along the timelines set for SAEs (even though they may not be classified as serious), ie, within 24 hours of the investigator's awareness, as described in [Appendix 4](#).

AESI are:

- Hypersensitivity reactions. Symptoms of hypersensitivity reactions (allergic reactions) include:
 - Rash
 - Wheezing and difficulty breathing
 - Dizziness and fainting
 - Swelling around the mouth, throat or eyes
 - A fast pulse
 - Sweating

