3.3 Appendix 3: Clinical Laboratory Tests

- The tests detailed in [Section 2.15.1](#) and the table below ([Table 4](#)) will be performed locally at the study site and sent to the central laboratory for analysis with the exception of urine pregnancy tests, which will be performed and analyzed locally at the site.
- Additional tests may be performed at any time during the study as determined necessary by the investigator or required by local regulations.

Investigators must document their review of each laboratory safety report.

The laboratory parameters to be analyzed are defined below in [Table 4](#). The time points of analysis are at Screening and EOS as defined in the SoA ([Section 2.15.1](#)). All labs are expected to be random (non-fasting).

Additional local laboratory tests may be performed as deemed appropriate by the Investigator (eg, in case of signs of any toxicity).

Table 4 Clinical Laboratory Tests

CHEM 20	CBC	Urinalysis
Glucose	Hemoglobin	Sp. Gravity (SG)
Sodium	Hematocrit	pH
Potassium	MCV	Leukocyte esterase
Carbon dioxide	MCH	Nitrites
Chloride	Red Cell Count	Hemoglobin
BUN	White Cell Count	Protein (Total)
Creatinine	Neutrophils (%)	Glucose
Calcium	Total Lymphs (%)	Ketones
Iron	Monocytes (%)	Urobilinogen
Albumin	Eosinophils(%)	Bilirubin
Total protein	Basophils (%)	
ALP	Neutrophils (Abs)	
ALT (SGPT)	Total Lymphs (Abs)	
AST (SGOT)	Monocytes (Abs)	
LDH	Eosinophils(Abs)	
GGT	Basophils (Abs)	
Bilirubin (total)	Platelets	
Uric acid		
Amylase		
Lipase		

3.4 Appendix 4: AEs and SAEs: Definitions and Procedures for Recording, Evaluating, Follow-up, and Reporting

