3.4.2 Events Meeting the AE Definition

- Any abnormal laboratory test results (hematology, clinical chemistry, or urinalysis) or other safety assessments (eg, radiological scans, vital signs measurements), including those that worsen from BL, considered clinically significant in the medical and scientific judgment of the Investigator (ie, not related to progression of underlying disease).
- Exacerbation of a chronic or intermittent pre-existing condition including either an increase in frequency and/or intensity of the condition.
- This includes progression of DR New conditions detected or diagnosed after study intervention administration even though it may have been present before the start of the study.
- Signs, symptoms, or the clinical sequelae of a suspected intervention-intervention interaction.
- Signs, symptoms, or the clinical sequelae of a suspected overdose of either study intervention or a concomitant medication. Overdose per se will not be reported as an AE/SAE unless it is an intentional overdose taken with possible suicidal/self-harming intent. Such overdoses should be reported regardless of sequelae.

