3.4.3 Events NOT Meeting the AE Definition

- Any clinically significant abnormal laboratory findings or other abnormal safety assessments which are associated with the underlying disease, unless judged by the Investigator to be more severe than expected for the participant's condition.
- The disease/disorder being studied or expected progression, signs, or symptoms of the disease/disorder being studied, unless more severe than expected for the participant's condition.
- Medical or surgical procedure (eg, endoscopy, appendectomy): the condition that leads to the procedure is the AE.

- Situations in which an untoward medical occurrence did not occur (social and/or convenience admission to a hospital).
- Anticipated day-to-day fluctuations of pre-existing disease(s) or condition(s) present or detected at the start of the study that do not worsen.

An SAE is defined as any AE that, at any dose:

a. Results in death

b. Is life-threatening

- The term 'life-threatening' in the definition of 'serious' refers to an event in which the participant was at risk of death at the time of the event. It does not refer to an event, which hypothetically might have caused death, if it were more severe.

c. Requires inpatient hospitalization or prolongation of existing hospitalization

- In general, hospitalization signifies that the participant has been admitted (usually involving at least an overnight stay) at the hospital or emergency ward for observation and/or treatment that would not have been appropriate in the physician's office or outpatient setting. Complications that occur during hospitalization are AEs. If a complication prolongs hospitalization or fulfills any other serious criteria, the event is serious. When in doubt as to whether "hospitalization" occurred or was necessary, the AE should be considered serious.
- Hospitalization for elective treatment of a pre-existing condition that did not worsen from BL is not considered an AE.

d. Results in persistent or significant disability/incapacity

- The term disability means a substantial disruption of a person's ability to conduct normal life functions.
- This definition is not intended to include experiences of relatively minor medical significance such as uncomplicated headache, nausea, vomiting, diarrhea, influenza, and accidental trauma (eg, sprained ankle) which may interfere with or prevent everyday life functions but do not constitute a substantial disruption.

e. Is a congenital anomaly/birth defect

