**3.2 Endpoints**

**3.2.1 Primary Endpoint - Safety**

The primary safety outcome measure of the study will be the proportion of participants who develop TEAEs through Week 24.

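### Protocol 2.17.3 can be read as making a normal-to-abnormal laboratory shift at end of study an AE without clinical judgment, while Appendix 4 requires that judgment, so the any-TEAE primary safety endpoint has two possible counting rules

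*Protocol*

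**What the plan says.** - **Protocol 2.17.3** requires clinically significant laboratory changes to be recorded, and extends the instruction with the words "including any lab test that was in the age-adjusted normal range and became abnormal at EOS, occurring during the study as an AE". The next paragraph adds a carve-out: "Abnormal laboratory findings associated with the underlying disease are not considered clinically significant unless judged by the investigator to be more severe than expected".
- **Protocol Appendix 4, 3.4.2** counts abnormal laboratory results as AEs, "including those that worsen from BL, considered clinically significant in the medical and scientific judgment of the Investigator". Section 3.4.3 repeats the underlying-disease exclusion.
- **Protocol 2.18** refers the reader to Appendix 3 for the AE and SAE definitions. Appendix 3 is the list of laboratory tests; the definitions are in Appendix 4.
- **Protocol 2.21.5 and SAP 4.11.1** define a TEAE by onset at or after dosing on Day 1. SAP 3.2.1 states: "The primary safety outcome measure of the study will be the proportion of participants who develop TEAEs through Week 24".
- **Protocol 2.21.3 and SAP 4.11** plan no inferential statistics for safety.
- **Protocol 2.21.7 and SAP 4.11.2** plan shift tables to out-of-range values, with listings for urinalysis and HbA1c.

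**The concern.** In 2.17.3 the word that introduces the clause places a normal-to-abnormal shift inside the class of clinically significant changes, so the range flag itself appears to settle the matter. In 3.4.2 the flag is only a starting point and the investigator decides. A sodium value one unit out of range at Visit 8 is an AE under the first rule and normally not under the second. Neither section says which prevails, and a site that follows the pointer in 2.18 lands on the test list and not on 3.4.2.

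At stake is how the primary safety proportion can be interpreted. Under the literal rule it would include chance laboratory variation unrelated to diabetes or to the drug. If sites split between the two rules, it would also include differences between sites in recording practice.

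**Working it through.** **Step 1. Does a recorded shift reach the endpoint?** Laboratory samples are taken at screening and Week 24 only (Protocol 2.17.3 and Schedule of Activities), so each test has one opportunity to shift. An AE arising from the Week 24 sample has onset after Day 1 dosing and is a TEAE. Neither SAP 3.2.1 nor 4.11.1 sets laboratory-only AEs apart. It counts.

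**Step 2. How many tests?** Protocol Table 4 lists 20 chemistry, 17 CBC and 10 urinalysis results. With HbA1c that is 20 + 17 + 10 + 1 = 48. I use the 20 + 17 = 37 chemistry and CBC tests, because several urinalysis results and HbA1c are close to the underlying disease.

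**Step 3. Per-test chance of a shift.** The plan states no shift rate and no expected TEAE rate, so there is no figure of its own to reproduce. Assume reference limits that cover the central 95%, normally distributed values, no drug effect, and correlation rho between a person's two results on the same test. Then q = 0.95 − P(in range at both visits):

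| rho | q | 1 − (1 − q)^37, independent tests |
|---|---|---|
| 0.5 | 4.07% | 79% |
| 0.7 | 3.35% | 72% |
| 0.9 | 2.04% | 53% |

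**Step 4. Allow for correlation between tests.** Tests in one person move together (hemoglobin with hematocrit, for example). Simulation with a common between-test correlation r, 20,000 participants per setting (Monte Carlo standard error at most √(0.25/20,000) = 0.35 points), gives the proportion with at least one shift among 37 tests:

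| r | rho 0.5 | rho 0.7 | rho 0.9 |
|---|---|---|---|
| 0.2 | 72% | 66% | 50% |
| 0.4 | 59% | 54% | 40% |
| 0.6 | 42% | 38% | 30% |

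The range is 30% to 72%.

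**Step 5. Sensitivity to the carve-out.** If seven of the 37 tests were set aside as disease-related, independent tests give 1 − (1 − q)^30 = 71%, 64% and 46% for rho 0.5, 0.7 and 0.9. These compare with 79%, 72% and 53% in Step 3.

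**Step 6. Effect on a contrast.** If a fraction b of every arm has a chance laboratory AE, independent of other TEAEs, a true rate p becomes 1 − (1 − p)(1 − b), and a difference is multiplied by (1 − b). For assumed true rates of 30% (vehicle) and 50% (active):

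- b = 0.30: 1 − 0.7 × 0.7 = 51% and 1 − 0.5 × 0.7 = 65%; 20 points become 14.
- b = 0.72: 1 − 0.7 × 0.28 = 80.4% and 1 − 0.5 × 0.28 = 86%; 20 points become 5.6.

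**Step 7. After the fix.** If only judged-significant shifts count, at an assumed 0.1% to 0.5% per test, 1 − (1 − q)^37 is about 4% to 17%. The like-for-like figure from Step 3 (independent tests) is 53% to 79%.

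**The case against.** The strongest reply is that there is no conflict. The instruction in 2.17.3 opens with clinically significant changes, and those words can be taken to govern the whole sentence, with shifts as an example of what to consider. On that reading 2.17.3 agrees with 3.4.2. This stands as a possible reading, and it is why the point is an ambiguity and not a proven contradiction. It does not remove the problem, because the grammar supports the literal reading at least as well and nothing tells a site which to apply.

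A reader might infer that every shift becomes an AE. The documents do not support that: the carve-out in 2.17.3 and 3.4.3 excludes findings associated with the underlying disease unless they are judged more severe than expected. It does not reach chance shifts in tests such as sodium or platelets.

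A reader might also infer that safety evaluation as a whole is overwhelmed, or that one arm is favoured. Neither follows. Chance shifts should occur alike in all arms, no safety test loses power because none is planned, and TEAEs are also tabulated by SOC and PT, intensity and relationship. For an eye drop the study-eye ocular tables matter most, and blood results do not enter them. What is diluted is the any-TEAE headline and the non-ocular totals.

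Finally, with only two laboratory time points, broad capture may have been intended. If so, 3.4.2 needs to say so.

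**Conclusion.** The point holds as an ambiguity with consequences for a primary endpoint. Sections 2.17.3 and 3.4.2 can be applied as two different rules, and the resulting AEs enter the any-TEAE proportion with no rule in the SAP to separate them. Under the literal rule at every site, about 30% to 72% of participants would have at least one chance shift among the 37 tests. The effect is inflation in all arms and dilution of any contrast, plus noise if sites differ.

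That range rests on assumptions the documents neither give nor contradict: 95% reference limits, within-person correlation 0.5 to 0.9, between-test correlation 0.2 to 0.6, and uniform use of the literal rule. A higher figure is tempting: treating a person's two results as unrelated gives 0.95 × 0.05 = 4.75% per test and 83% over 37 independent tests. I do not rely on it, because repeat results in one person are normally correlated. Participants already out of range at screening cannot shift on that test; q allows for this at 5% per test, but a higher screening abnormality rate in this population would change it. Confidence is high that the wording permits two rules and moderate on the size.

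**What to change.** 1. **Protocol 2.17.3:** delete the clause on tests that were normal and became abnormal at EOS, or qualify it with a condition that the investigator judges the change clinically significant, so that 3.4.2 is the single rule. If broad capture was intended, the sponsor should say so in both sections.
2. **Protocol 2.18:** change the pointer for AE and SAE definitions from Appendix 3 to Appendix 4.
3. **SAP 4.11.1, if shifts have already been recorded as AEs:** add a supplementary TEAE proportion that excludes laboratory-only AEs. Identify these events at the masked data review (SAP 4.4.1), before database lock.

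The cost is one protocol clause or a site clarification, one corrected reference, and possibly one supplementary summary. That summary needs a small masked review, because the AE attributes listed in Protocol 2.21.5 and SAP 4.11.1 include no clinical-significance flag. Fewer non-significant laboratory AEs will be recorded. Hematology and chemistry shifts stay visible in the planned shift tables, and urinalysis and HbA1c in the listings. The efficacy sample size is not affected.
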